#### Investigations:

Following the recruitment procedure and after giving the formal informed consent, all study participants will undergo clinical and hearing assessments and complete a set of validated hearing and quality-of-life questionnaires (detailed description below). In addition, the siderosis participants will undergo assessments of the balance (including balance questionnaires) and olfactory functions, and saliva sampling (in an anonymised format) for DNA banking for iSS. The anonymised saliva samples may be used for other/future research studies. Results of cognitive, imaging and other clinical assessments will be performed as part of the clinical care pathway and will not be assessed as part of this research project. However, their results may be used in the anonymised format as part of this research study.

The ARHL group and the control group participants will require one assessment session whereas the siderosis group participants will require three sessions in total (two of which will be standard part of the clinical care pathway).

#### Siderosis group visits and investigations:

Siderosis group participants will be seen by the clinical team as part of their clinical care pathway and will undergo the following tests during their **first/initial visit in the Neuro-otology clinic:**

1. *Informed consent*
2. *Full neuro-otological examination:* full medical history; clinical examination of the head and neck, ears (otoscopy) and cranial nerves III/IV/VI/VII, (20mins)
3. *Pure tone audiometry (PTA)* for each ear measuring air and bone-conduction (15mins)
4. *Screening tympanogram* to check the function of the middle ear (5mins)
5. *Auditory Brainstem response (ABR) testing* on a calibrated ABR system; recorded with monaural alternating click stimuli; minimum intensity of 90dB (40mins)
6. *Vestibular nystagmography (VNG)/rotational chair testing:* including eye tracking/gaze nystagmus/positional nystagmus/optokinetic nystagmus/smooth pursuit/saccade tests (30mins)

7. *Video Head Impulse Test (vHIT)*: using appropriate software, goggles and in-built video-camera to record eye movements during unpredictably-timed and -directed head-rotations at speed 150-300degree/s (10mins)

At the first clinic visit the siderosis group the participants who have expressed interest in participating in the study will be seen by the research student. After confirming their eligibility and willingness to participate in the study, the potential participants will be formally consented and enrolled in the study. The research student and the study participant will arrange a suitable date/time for the research visit to take place.

During the research visit, the siderosis group participants will undergo the following:

1. Verification of the participant's eligibility to participate in the study and that the informed consent has been obtained (5mins)
2. Brief medical history and clinical examination (of ears/eyes/co-ordination) (5mins)
3. *Speech-in-quiet test* (10mins)
4. *Otoacoustic emissions (OAEs)* by delivering sound stimuli through a probe in the ear canal, using dual channel analyser (10mins)
5. *Stapedial (acoustic) reflex thresholds*: ipsilateral (same side) and contralateral (opposite side) measurements using a calibrated middle ear recorder at 0.5/1/2/4 kHz; range 70-120dB HL (5mins);
6. *Speech-in-noise testing*: a set of tests with background noise/speech/babble, administered using appropriate programme through headphones, where words/sentences/speech presented in competing background noise/speech/babble (50-60mins)
7. *Functional Gait Assessment (FGA)*: assessment of postural stability; 10-point test, incorporating (head) turns, gait changes (that would usually include speed, narrow base, stairs, backwards, level, obstacles) (10mins)
8. *Scale for Assessment and Rating of Ataxia (SARA)*: clinical scale to assess cerebellar ataxia which is made up of 8 items related to gait, stance, sitting, speech, finger-chase test, nose-finger test, fast alternating movements and heel-shin test (15mins)
9. *Olfactory (smell) Smell Identification Test (SIT)*: self-administered test, a booklet with odour-impregnated pages; the odour is introduced to the tester by scratching the test booklets (10mins)
10. *Saliva sampling* for DNA biobanking (max 30ml, equivalent of the volume of maximum two table-spoons) (5mins)

11. *Hearing questionnaires* (which can be distributed to the participant ahead of the appointment and collected during their visit, after having given formal consent to participate in the study, as a time saving measure)

- *Modified Amsterdam Inventory for Auditory Disability and Handicap (mAIDH) questionnaire*: a 28-point self-report questionnaire that assesses listening ability on 5 domains (5mins)
- *Speech, Spatial and Qualities of Hearing Scale (SSQ) questionnaire*; contains 50 items and involves 3 hearing domains, namely: speech, spatial and qualities (of sound segregation and identification) (5mins)
- *Tinnitus Functional Index (TFI) questionnaire*; 25-item self-report questionnaire; has been shown to have higher validity than other tinnitus questionnaires (5mins)

12. *Vestibular questionnaires* (which can be distributed to the participant ahead of the appointment and collected during their visit, after having given formal consent to participate in the study, as a time saving measure) and will include:

- *Dizziness Handicap Inventory (DHI)*: self-report questionnaire on perceived impact of dizziness on daily life assessing (5mins)
- *Situational Vertigo Questionnaire (SVQ)*: self-report 19-item questionnaire that measures frequency of symptoms of disorientation/vertigo against visually busy environment (5mins)

13. *Quality-of-life questionnaires* (which can be distributed to the participant ahead of the appointment and collected during their visit, after having given formal consent to participate in the study, as a time saving measure). The quality of life will be assessed using three validated quality-of-life questionnaires:

- *Health Utilities Index-3 (HUI3)* (5mins)
- *EuroQoL Questionnaire (EQ-5D-5L)* (5mins)
- *Evaluation of the Impact of Hearing Loss in Adults (ERSA)*

A follow-up clinical appointment will be also arranged for the siderosis patients (irrespective of their participation in the study). During their follow-up clinical visit, the siderosis patients will undergo the following clinical assessments, as part of their clinical care:

1. *Vestibular evoked myogenic potentials (VEMP)*: calibrated auditory stimuli via ear inserts repetitively presented and neck/eye myogenic (muscle) responses are recorded (20mins)

2. The siderosis patients who have previously consented to participate in the study will then be seen by the research student and the *questionnaires* previously distributed to the study participants will be collected (5mins)

Appropriate break times will be given to the participants during their research study visit. It is anticipated that the total time to complete the assessments will be approximately two to three hours for each visit.

Where the research tests have been completed by the audiologist/clinician/nurse, the research student shall not repeat those during the respective visit but will instead include the results of the tests already performed. Where the clinical tests have not been carried out by the clinical staff (audiologist/clinician/nurse), the research student will carry these out as part of the clinical care pathway and will include the results obtained from the clinical assessments.

Cognitive function will be assessed by means of neuro-psychological testing in line with the clinical care pathway and will be arranged by the clinical team. Imaging will be arranged by the clinical team in line with the clinical care pathway for siderosis patients. With the prior consent obtained from the participants, the results of the clinical assessments (including cognitive and imaging tests) will be obtained and anonymised at source.

Age-related hearing loss group and control group participants' visits and investigations:

The age-related hearing loss group and control group participants will undergo the clinical and hearing assessment (including hearing questionnaires) and quality-of-life questionnaires during one visit only. All the tests will be done as part of this research study.

During their visit, the ARHL group and control group participants will undergo:

1. Informed consent
2. *Full neuro-otological examination* (full medical history; clinical examination of the head and neck, ears (otoscopy) and cranial nerves III/IV/VI/VII)
3. *Pure tone audiometry (PTA)*, for each ear measuring air and bone-conduction (15mins)
4. *Otoacoustic emissions (OAEs)*, by delivering sound stimuli through a probe in the ear canal, using dual channel analyser (10mins)
5. Speech in quiet test (10mins)
6. *Stapedial (acoustic) reflex thresholds*: ipsilateral and contralateral measurements using a calibrated middle ear recorder at 0.5/1/2/4 kHz; range 70-120dB HL (5mins);

7. *Auditory brainstem evoked response (ABR) testing*, on a calibrated ABR system; recorded with monaural alternating click stimuli; minimum intensity of 90dB (40mins)
8. *Speech in noise testing*, a set of tests with background noise/speech/babble, administered using appropriate programme through headphones, where words/sentences/speech presented in competing background noise/speech/babble (50-60mins)
9. *Hearing questionnaires* (which can be distributed to the participant ahead of the appointment and collected during their visit, after having given formal consent to participate in the study, as a time saving measure), including:
  - *Modified Amsterdam Inventory for Auditory Disability and Handicap (mAIDAH) questionnaire*: a 28-point self-report questionnaire that assesses listening ability on 5 domains; (5mins)
  - *Speech, Spatial and Qualities of Hearing Scale (SSQ) questionnaire*; contains 50 items and involves 3 hearing domains, namely: speech, spatial and qualities (of sound segregation and identification) (5mins)
  - *Tinnitus Functional Index (TFI) questionnaire*; 25-item self-report questionnaire; has been demonstrated to have higher validity than other tinnitus questionnaires (5mins)
10. *Quality-of-life questionnaires* (which can be sent out to the participant ahead of the appointment and collected during their first visit, after having given formal consent to participate in the study, as a time saving measure). The quality of life will be assessed using two standard quality-of-life questionnaires:
  - *Health Utilities Index-3 (HUI3)* (5mins)
  - *EuroQoL Questionnaire (EQ-5D-5L)* (5mins)
  - *Evaluation of the Impact of Hearing Loss in Adults (ERSA)*

Appropriate break times will be given to the participants during their testing at the research study visit. It is anticipated that the total time to complete the assessments will be approximately two to three hours.

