We also hypothesise that there will be a greater deficit in speech-in-noise tests in iSS group compared with the ARHL and the control groups, when controlling for hearing deficits and that the speech-in-noise tests are better predictors of hearing dysfunction in iSS than PTA alone or with speech-in-quiet testing. We thus anticipate that speech-in noise tests will account for greater auditory deficits and will better correlate with patient-reported auditory difficulties than PTA and speech-in-quiet tests. We also anticipate a words-in-background babble test will be more able to predict auditory and cognitive impairment in iSS patients than a words-in-background speech noise.

Due to limited volume of literature that describes vestibular function in iSS and its heterogeneity in the battery of tests used, there is a need to provide a comprehensive description of vestibular function in these patients. We hypothesise that balance dysfunction will be due to a mixed (peripheral and central) vestibular deficits and that there will be a greater number of central and oculo-motor abnormalities detected in iSS patients when compared to normative data (40, 41). We also hypothesise that audiovestibular dysfunction will be identified in the majority of iSS patients after the initial radiological diagnosis and that these deficits will correspond to the involved structures of the auditory and vestibular pathways as visualised on brain images. Correlating the findings of assessments performed with the brain imaging would increase our understanding of the role of imaging in identification of the involved structure(s) of the audiovestibular pathways in iSS. Additionally, other clinical parameters may also be reflective of the symptom load or the degree of audiovestibular dysfunction and disease progression, and we would like to correlate the results of clinical tests performed in the clinical setting, including MRI, with the audiovestibular findings.

It is likely that iSS and its associated progressive and debilitating hearing and balance impairment) have a negative impact on quality of life. To our knowledge, this has not been reported in the literature and further studies are required to determine this. We will therefore assess the impact of iSS on the quality of life in patients with iSS.

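### If the listed test orders are followed, speech-in-noise starts about 45-75 minutes later in the ARHL/control visit than in the siderosis research visit, so position in the session is confounded with group

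*Combined protocol and SAP*

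**What the plan says.** Section 2 (Rationale) hypothesises a "greater deficit in speech-in-noise tests in iSS group compared with the ARHL and the control groups, when controlling for hearing deficits". Section 4.2 then asks which audiological tests better predict impairment in iSS against both comparators.

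Section 5.2 describes the sessions separately by group:

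- **Siderosis.** PTA and ABR are listed for the first clinic visit. The research visit is booked separately: "The research student and the study participant will arrange a suitable date/time for the research visit to take place". Speech-in-noise is item 6 of that visit. The items before it are "Verification of the participant's eligibility to participate in the study and that the informed consent has been obtained (5mins"), "Brief medical history and clinical examination (of ears/eyes/co-ordination) (5mins"), "Speech-in-quiet test* (10mins"), otoacoustic emissions ("by delivering sound stimuli through a probe in the ear canal, using dual channel analyser (10mins")) and stapedial reflexes ("using a calibrated middle ear recorder at 0.5/1/2/4 kHz; range 70-120dB HL (5mins")).
- **ARHL and control.** Everything is done in one visit. Speech-in-noise is item 8, after consent, the full neuro-otological examination, PTA, otoacoustic emissions, speech in quiet, reflexes and a 40-minute ABR.

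The speech-in-noise block has the same description and length in both lists: "administered using appropriate programme through headphones, where words/sentences/speech presented in competing background noise/speech/babble (50-60mins"). Breaks are promised in both visits, but with no number, length or timing. No section declares the numbering binding, randomises or counterbalances the order, or asks for the start time of speech-in-noise to be recorded.

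**The concern.** Speech-in-noise is a listening task of close to an hour, and performance on it plausibly depends on sustained attention. The two lists place it at different points of the session, and which list a participant follows is decided by group. Under those lists the siderosis-versus-comparator contrast is also an early-versus-late contrast. The regression models in section 5.5 could not separate the two, because start position would hardly vary within a group.

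At stake is the reading of one of the study's main hypothesised comparisons. If testing later in a session lowers scores, the ARHL and control groups are penalised and a true iSS deficit looks smaller than it is. With 20-30 participants per group there is little room for such a loss.

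**Working it through.** The protocol states no start time for speech-in-noise, so there is no figure of its own to reproduce. Elapsed time is the sum of the listed durations before that item, in list order, without breaks.

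**Siderosis research visit** (section 5.2, items 1-5): eligibility and consent check 5, brief history and examination 5, speech-in-quiet 10, otoacoustic emissions 10, reflexes 5.
5 + 5 + 10 + 10 + 5 = **35 min**.

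**ARHL/control visit** (section 5.2, items 1-7):

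- Printed times only: PTA 15, otoacoustic emissions 10, speech in quiet 10, reflexes 5, ABR 40. 15 + 10 + 10 + 5 + 40 = **80 min**.
- The full examination has no duration in this list. Assumption: the 20 min given for the same examination in the siderosis clinic list. 80 + 20 = **100 min**.
- Consent has no duration. Assumption: 5 min. 100 + 5 = **105 min**.
- Appendix 2 marks a screening tympanogram for these groups, although the section 5.2 list omits it. Assumption: it comes before speech-in-noise and takes the 5 min of the siderosis clinic list. 105 + 5 = **110 min**.

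**Gap in start time:**

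- Printed times only: 80 - 35 = **45 min**.
- With the examination: 100 - 35 = **65 min**.
- With examination, consent and tympanogram: 110 - 35 = **75 min**.

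**End of speech-in-noise** (50-60 min long): siderosis 35 + 50 = 85 to 35 + 60 = 95 min; ARHL/control, from a 100-minute start, 150 to 160 min.

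**Share due to ABR:** 40 min in every version. With ABR after the speech tests, the ARHL/control start becomes 80 - 40 = 40, 100 - 40 = 60 or 110 - 40 = 70 min, and the gap becomes 40 - 35 = **5**, 60 - 35 = **25** or 70 - 35 = **35 min**.

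**Active listening before speech-in-noise:** siderosis 10 min (speech-in-quiet); ARHL/control 15 + 10 = 25 min (PTA and speech in quiet). The difference is 15 min.

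No loss of power is computed. The documents give no fatigue effect, standard deviation or target difference, and section 7.2.1 says that power cannot be reliably calculated in advance, so any such figure would only restate assumptions.

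**The case against.** The case on the other side has real substance.

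- **The lists may not be running orders.** The numbering is not declared a sequence. Speech-in-quiet and otoacoustic emissions swap places between the two lists, and Appendix 2 uses another arrangement. The research student may also carry out clinical tests that clinic staff missed. This stands, and it makes the finding conditional. But the lists are the only sequence offered, and an order left open does not equalise position either.
- **A separate day is inferred.** The text speaks of a separately arranged visit, not a different day. If a participant chose the same day, the clinic list of 20 + 15 + 5 + 40 + 30 + 10 = 120 min could come first. Speech-in-noise would then start at 120 + 35 = 155 min and the gap would reverse. This stands as a further source of uncontrolled timing.
- **Minutes are not fatigue.** ABR is passive and makes up 40 of the 45-75 minutes; the difference in active listening is only 15. Participants with iSS may also tire sooner: section 2 cites cognitive impairment in 20 percent of patients. Both points stand, so neither the size nor the direction of an effect is known.
- **The plan is not silent on flow.** Breaks are promised, section 8.2 (Training) plans a meeting of researchers on uniform steps, and section 8.4 seeks public views on appointment length and timing. None of these sets a common order or a common break.

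A reader might infer that fatigue does differ between groups, that the study's key outcome is biased, and that no adjustment could repair it. The documents do not support this. No fatigue measure or effect is given. Speech-in-noise is a named hypothesis but not a designated primary outcome (section 7.2.1 names no gold-standard test, and the primary question in section 4.2 covers the whole profile). Complete confounding would need the listed order never to vary.

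**Conclusion.** The concern holds as a conditional design risk. If the listed orders are followed, speech-in-noise starts about 35 minutes into the siderosis research visit and about 80-110 minutes into the ARHL/control visit. The 35 and the 80 are sums of printed times; anything above 80 rests on the assumed durations shown. Nothing in the plan sets a common order or break timing, so session position is confounded with group on a main hypothesised comparison.

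Fatigue may differ by group, but that is a possibility and not an established difference. If later testing does lower scores and the groups tire alike, the bias runs against the study's own hypothesis: it would hide part of an iSS deficit, not create one. The point deserves a change because the stated sequence produces the imbalance, and a start time that is not recorded cannot be recovered afterwards.

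**What to change.** In section 5.2:

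1. State one order for speech-in-quiet and speech-in-noise that applies to all three groups, and say that it is to be followed.
2. In the ARHL/control visit, place ABR after the speech tests.
3. Set the same break before speech-in-noise in every group, to deal with the remaining 5-35 minutes.
4. Record the start time of speech-in-noise and what was done before it that day, so that same-day clinic testing or a changed order is visible and can be examined in a sensitivity analysis.

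The cost is minor rescheduling within the existing visit and one more recorded item. No test or staff is added.

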#### Follow-up Investigations:

As a follow-up measure, all study participants will undertake a repeat set of self-report questionnaires after 12 months of their initial completion of the questionnaires (as what would have been completed by the participants at the beginning of the study). These will be sent out to the participants with pre-stamped self-addressed envelopes and will be returned to the research facility by post, or distributed and collected electronically.

The assessments of the siderosis group participants will take place at University College London Hospitals (NHS Foundation Trust). The assessments of the participants from the ARHL group and control group will take place at University College Hospitals (NHS Foundation Trust) London and/or the UCL Ear Institute, depending on the availability of the testing facilities.

The data will be collected and analysed using a dedicated statistical software programme (package) to determine disease-specific pattern and test deficits in iSS and to compare those to the ARHL and the control groups and to the normative data (vestibular function only).

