**Comparison:**

The findings obtained following the audiological and the quality-of-life questionnaires will be compared between the siderosis group, the ARHL group, and the control group. The results of vestibular assessments will be compared to the age-matched normative data.

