## 5.5 Data analysis methods

Quantitative Analysis will be conducted using dedicated statistical software package.

Statistical analysis will be performed under the guidance and with advice of a designated biostatistician at UCL and/or at Biostatistics Office, UCL(H) Joint Research Office (JRO).

Each variable will be checked for distribution skewness, and regression models for each variable will be constructed. For binary variables, chi-square tests will be performed in order to determine the difference in the findings between the siderosis group and the control groups.

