## 6. STUDY SETTING

After participant recruitment, the study assessments will take place at University College London Hospitals (NHS Foundation Trust) (participants from all groups) or UCL Ear Institute (participants from ARHL and control groups only). The participants for this study will be recruited from:

- University College London Hospitals (NHS Foundation Trust) (siderosis group)
- Adult Audiology Centre, University College London Hospitals (NHS Foundation Trust) (ARHL group)
- The general public (ARHL and control groups): will be recruited from University College London Hospitals (NHS Foundation Trust) waiting areas, canteens, cafeterias, BRC BioResource group, AgeUK group, the University of Third Age and dedicated Facebook/social network and online groups

The clinical equipment available at the Adult Audiology Services at University College London Hospitals (NHS Foundation Trust) or provided by the UCL Ear Institute, will be used to conduct this study. No additional equipment will be provided to sites for the purposes of the study since all the tests in this protocol are already available to the NHS users with hearing impairment, poor coordination or cognitive impairment. The facilities at the Ear Institute permit hearing tests to take place. These can be conducted by the research student and be undertaken by the participants with minimal risk of balance problems and minimal risks of falls such as the ARHL group and control group participants.

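### Only the comparator groups may be tested at the Ear Institute, so any site or device difference would bias the siderosis hearing contrasts, and the plan neither limits nor examines it

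*Combined protocol and SAP*

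**What the plan says.** Section 5.2 (Follow-up Investigations) sets the places of testing. For the siderosis group, "The assessments of the siderosis group participants will take place at University College London Hospitals (NHS Foundation Trust". The ARHL and control groups may be seen at the hospital "and/or the UCL Ear Institute, depending on the availability of the testing facilities". The Study/Participant Timeline repeats this. Section 6 lists the hospital for all groups and the "UCL Ear Institute (participants from ARHL and control groups only". It names two sources of equipment, the hospital's Adult Audiology Services or equipment "or provided by the UCL Ear Institute, will be used to conduct this study". It also gives a reason for the restriction: the Ear Institute suits people "with minimal risk of balance problems and minimal risks of falls such as the ARHL group and control group participants".

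Under Comparison in section 5.2, the audiological findings "will be compared between the siderosis group, the ARHL group, and the control group", while vestibular results are set against normative data. On analysis, section 5.5 says: "Each variable will be checked for distribution skewness, and regression models for each variable will be constructed". It names no covariate and no site or device term.

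Some test settings are common to all groups in section 5.2: alternating monaural clicks for ABR, the reflex frequencies and level range, and calibrated devices for those two tests. The Training paragraph of section 8.2 adds a meeting of researchers before the study starts.

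**The concern.** Thresholds, emission levels, reflexes, ABR and headphone speech scores can all depend on the transducer, the settings and the room. If the two sites differ on any of these, the comparator means move and the siderosis means do not. The shift would then be read as a feature of the disease, or would hide one. More participants would not reduce it.

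The comparisons at risk include the auditory part of the primary question and the tertiary question (section 4.2), and the Rationale's hypothesis of a larger speech-in-noise deficit in siderosis. Siderosis versus ARHL is the more exposed contrast: the Background and Rationale describe the two audiograms as similar, so the differences sought may be modest.

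**Working it through.** **Inputs.** Group size is 20 to 30 (Study Summary; section 7.3). The siderosis share at the Ear Institute is 0 (section 6). The comparator share *f* is not stated and can be anything from 0 to 1. The offset *d* (Ear Institute minus hospital, in SD units) is not stated; 0, 0.2, 0.3 and 0.5 are assumed here. A two-sided 5% test is also assumed. The plan gives no alpha, SD or effect size, and section 7.2.1 says that no reliable power calculation is possible, so there is no figure of the plan's own to reproduce.

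**Step 1: bias.** The comparator mean shifts by *f* × *d* and the siderosis mean by 0, so the size of the bias in the contrast is *f* × *d*. With *d* = 0.3 it is 0.15 SD at *f* = 0.5 and 0.30 SD at *f* = 1. It is zero if either *f* or *d* is zero. The ARHL-versus-control contrast is biased only if those two groups have different shares.

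**Step 2: false-positive rate with no true difference.** SE = √[1/n + (1 + *f*(1−*f*)*d*²)/n], and the rate is 1 − Φ(1.96 − *fd*/SE) + Φ(−1.96 − *fd*/SE). For example, with n = 20, *f* = 0.5 and *d* = 0.3, SE = 0.318, *fd*/SE = 0.47 and the rate is 7.6%.

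| n per group | *f* | *d* = 0 | *d* = 0.2 | *d* = 0.3 | *d* = 0.5 |
|---|---|---|---|---|---|
| 20 | 0.5 | 5% | 6.1% | 7.6% | 12.2% |
| 20 | 1 | 5% | 9.7% | 15.8% | 35.3% |
| 30 | 0.5 | 5% | 6.7% | 8.9% | 15.9% |
| 30 | 1 | 5% | 12.1% | 21.3% | 49.1% |

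At *f* = 0 every entry is 5%. The rates rise with n because the bias stays the same while the SE falls.

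**Step 3: what a later analysis could recover.** Take a model with intercept, two group terms and a site term, and the same *f* in both comparator groups. The offset is estimated within those groups with variance 1/[2n*f*(1−*f*)] (SD = 1). The adjusted contrast then has variance 2/n + *f*²/[2n*f*(1−*f*)] = (2/n) × {1 + *f*/[4(1−*f*)]}.

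- *f* = 0.5: 1 + 0.5/2 = 1.25 times the unadjusted variance. At n = 20 the SE goes from 0.316 to 0.354.
- *f* = 2/3: 1 + 0.667/1.333 = 1.5 times.
- *f* = 1: the design matrix has rank 3 of 4, and the contrast cannot be estimated.

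Restricting to hospital-tested participants gives variance 1/n + 1/[n(1−*f*)], which is {1 + 1/(1−*f*)}/2 times the full-sample variance: 1.5 at *f* = 0.5 and 2.0 at *f* = 2/3.

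**Step 4: how well the offset itself is estimated.** At *f* = 0.5 its SE is √(1/10) = 0.316 for n = 20 and √(1/15) = 0.258 for n = 30. The 95% half-widths are 0.62 and 0.51 SD. An offset of the sizes in the table would be estimated poorly, so preventing it is worth more than adjusting for it.

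**The case against.** The strongest reply is that no difference between sites has been shown. Section 6 names two equipment sources but does not say that devices or settings differ. That stands, and it is why the size can only be given as a range that includes zero.

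A reader might infer that site and disease are fully confounded. The documents do not support this. Section 6 lists the hospital for all groups, and hospital audiology is one source of ARHL participants. Full confounding needs every comparator to be tested at the Ear Institute, which the plan permits but does not intend. Section 8.6 and Appendix 1 also file paper records by place of testing, so site could be recovered and a mixed split could be analysed.

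The safeguards count for something but are partial. Calibration is stated for ABR and reflexes only. The ABR level is given as a minimum. The speech tests have no stated transducer or presentation level. A start-up meeting does not align hardware or rooms.

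For siderosis versus control on pure tone audiometry, a modest offset is unlikely to decide the result: the Background describes siderosis hearing loss as often moderate to severe, and controls have no known loss. This also stands.

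The absence of a site term is part of a wider gap, since section 5.5 names no covariates at all. And the hospital may not be a single device set: siderosis audiometry and ABR belong to the Neuro-otology clinic visit, and clinical results are reused. A site term alone could miss that, so device must be recorded too.

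The falls reasoning in section 6 explains why siderosis participants stay at the hospital. It does not require comparators to be tested elsewhere.

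**Conclusion.** The point holds as a conditional bias. Following the plan, any site or device offset enters the siderosis-versus-ARHL and siderosis-versus-control contrasts on instrument-dependent hearing tests, multiplied by the share of comparators tested at the Ear Institute. Nothing in the plan limits that share or examines the effect. The false-positive rates above rest on assumed offsets, an assumed 5% test and an unknown share; they show a range and are not a forecast.

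The documents do not establish that an offset exists, or any particular size for it. Self-report questionnaires and vestibular results are outside the point. The offset becomes inseparable from disease only at a share of 100%. This is a worthwhile, inexpensive improvement, best made before comparators are booked.

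**What to change.** 1. In section 5.2 (Follow-up Investigations), the Study/Participant Timeline and section 6, make the hospital the default site for ARHL and control testing, with the Ear Institute used only when no hospital slot is available. Siderosis arrangements do not change.
2. Use one settings sheet at both sites and in the clinic whose results are reused. It should cover transducer, ABR level, rate and averages, emissions protocol and speech presentation level.
3. Record site and device for every hearing test.
4. In section 5.5, add two sensitivity analyses of the group comparisons: one adjusted for site, and one restricted to hospital-tested participants. Report the share tested at each site by group.

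The cost is less flexible booking for comparators, two extra data fields and wider intervals in the sensitivity analyses. The site-adjusted variance is about 1.25 times the unadjusted variance at a 50% share and 1.5 times at two thirds; the hospital-only multiples are 1.5 and 2.0. That loss is the reason to keep the site term out of the main model. If all comparators are tested at the hospital, no precision is lost and the site difference disappears, though a device difference within the hospital could remain.
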